8.5.4.8 Social Provisions Scale (SPS)

The SPS a 24-item measure of the degree to which respondents' social relationships provide various dimensions of support [146]. The scale includes six subscales based on Weiss's (1974) social provisions theory: reliable alliance, attachment, nurturance, social integration, reassurance of worth, and guidance [147]. Each subscale has four items, two positively worded items and two negatively worded items assessing the absence of support. Questions are rated on a 4-point Likert-type scale with anchors of 1 (strongly disagree) and 4 (strongly agree). Cronbach's alpha coefficients of the six factors ranged from 0.67 to 0.76, and construct validity is supported. High correlation between the SPS and other measures of support provided evidence for the construct validity of the scale. The SPS takes approximately 5 minutes to complete.

8.5.4.9 Self-Compassion Scale (SCS)

The SCS is a 26-item self-report measure of self-compassion, or responding to one's own failure, suffering or inadequacies with kindness and compassion and recognizing one's own flaws and suffering as part of common human experience [148]. Respondents complete the SCS by indicating how typical they feel on each item on a 5-point Likert scale (1=Almost never and 5=Almost always). The scale has six sub-scales: Self-Kindness, Self-Judgment, Common Humanity, Isolation, Mindfulness, and Over-Identified. The mean of subscale scores serves as a total score. Analysis of SCS response indicated that subscales are all related to a higher order factor of self-compassion, and the measure has high test-retest reliability at a level of 0.93. Neff *et al.* reported an inverse relationship between SCS total scores and scores on measures of depression and anxiety. Self-compassion and global self-esteem are both related to positive mood and optimism, but self-compassion may be more strongly associated with stable mood and less associated with self-rumination and anger [149]. The SCS takes approximately 6 minutes to complete.

8.5.4.10 EuroQol Five Dimensions – Five Levels Questionnaire (EQ-5D-5L)

The EQ-5D-5L is a two-part self-report questionnaire assessing health status. It consists of five dimensions; mobility, self-care, usual activities, pain-discomfort and anxiety-depression, and one visual analog scale (VAS). Responses are made on each dimension by checking one of five statements that best reflects their health on the day of measure completion, from the healthiest or fewest problems (e.g., "I have no trouble walking about") to the most trouble (e.g., "I am unable to walk about") [150, 151]. In the second part of the EQ-5D-5L, current degree of health ("your health today") is indicated by marking a 100 mm line, with 100 considered "the best health you can imagine" and one "the worst health you can imagine". The EQ-5D-5L does not sum

responses but treats each response on a dimension as a scale score, and the VAS (Visual Analogue Scale) is the location of the mark. The scale can permit comparison across groups on health profiles, and an index can be derived from matching the five-dimension scores and the VAS response with nation-specific datasets and calculator software or statistical software syntax designed for the measure. The EQ-5D-5L began as part of the EuroQoL measure, published in 1990 [152]. The instrument has been validated in populations from eight countries. EQ-5D-5L index scores and VAS scores assessed in people with stroke varied with degree of recovery assessed via long-term observation [153]. The EQ-5D-5L takes approximately 3 minutes to complete.

8.5.4.11 Health and Work Performance Questionnaire Short Form (HPQSF)

The HPQSF is a short form of a larger measure of health and work performance that has selected items referring to absenteeism and work performance (Kessler, Ames et al. 2004). The larger measure was created by the WHO as part of the Global Burden of Disease initiative. It consists of eight questions selected from the larger Health and Work Performance Questionnaire, with one question containing five additional items. Items include questions concerning hours worked during an average week, number of whole and partial days missed during a 4-week period, and items that rate average coworker and self-work performance on a 10-point Likert scale (1=Worst performance to 10=Top performance). Hours spent in work over a 4-week period and over the last 7 days can be used to estimate absenteeism, and the HPQSF can also score presenteeism, a measure of actual performance in relation to possible performance. Self-reports on measure appear to match employer records of presence or absence (Kessler, Barber et al. 2003), and the HPQSF appears to be reliable between one time point and another (reliability of 0.52) and is sensitive to change (Kessler, Ames et al. 2004). The HPQSF takes approximately 5 minutes to complete.

8.6 Safety Assessments

Additional visits or repeat assessments (in person, at home, by telephone, or via tele-assessment) may be scheduled at the discretion of the study staff to collect more information for determining eligibility or to discuss study expectations with the potential participant.

8.6.1 Suicidal Ideation and Behavior Risk Monitoring

Suicidal ideation and behavior are disease related events with high incidence in populations of people with PTSD, especially those suffering from chronic PTSD. Participants will be monitored and observed closely for increases in suicidal ideation and behavior (SIB) or any other unusual changes in behavior. Participants are asked to report on their suicidality in therapy sessions and frequent phone calls. They may experience intense emotional responses to recalling and speaking about this material. Participants who experience increases in SIB should undergo a risk assessment.

Baseline assessment of suicidal ideation and behavior/intervention-emergent suicidal ideation and behavior will be monitored during the study using the MAPS Adapted C-SSRS.

8.6.1.1 MAPS Adapted Columbia-Suicide Severity Rating Scale (C-SSRS)

The C-SSRS is a clinician-administered measure of suicidal behavior devised to detect potential suicidal thoughts or behaviors during a clinical trial [154]. It consists of a Baseline/Screening

version and a Since Last Visit version that assess suicidal ideation, ideation intensity, and behavior. The C-SSRS consists of a series of questions and can be administered during a face-to-face interview or over the telephone. The Baseline/Screening version will only be administered at the initial Screening visit. All subsequent administrations will utilize the Since Last Visit version. Participants who are discontinuing medications to participate in the study will complete the C-SSRS before and after medication washout. The C-SSRS Intensity scale obtained a Cronbach's alpha of 0.94 for the Since Last Visit form, and Last Visit C-SSRS severity scores were positively correlated with the BDI "suicide thoughts" item [155]. The MAPS Adapted C-SSRS was developed utilizing [name] Columbia Suicide Severity Scale. The MAPS Adapted C-SSRS maintains the content and flow of the standard C-SSRS. The scale was adapted to modify formatting and add additional administrative guidance to reduce rater and data entry errors. The MAPS Adapted C-SSRS has been approved by [name] for use in MAPS Research and is referred to throughout the protocol as C-SSRS. The MAPS Adapted C-SSRS takes approximately 10 minutes to complete.

8.6.2 Physical Examinations

A physical examination will be symptom-directed and include, at a minimum, assessments of the cardiovascular, respiratory, gastrointestinal, and neurological systems. Traumatic Brain Injury (TBI) assessment with residual neurological signs or symptoms should be included as part of the neurological exam. Height and weight will also be measured and recorded, which will be used to calculate Body Mass Index (BMI). Investigators should pay special attention to clinical signs related to previous serious illnesses. A member of the therapy team should not perform the physical exam.

8.6.3 Vital Signs

Vital signs will be measured after 5 minutes rest in a semi-supine position and will include temperature, systolic and diastolic blood pressure, and pulse.

Additional at-home blood pressure measurements may be required to corroborate or rule out undiagnosed hypertension or to determine if an ongoing diagnosis of hypertension is controlled, and as required per the eligibility criteria of this protocol.

8.6.4 Electrocardiograms

12-lead ECG(s) will be obtained after 5 minutes of rest in a semi-supine position. ECGs will be collected in triplicate at the timepoints outlined in the SoA using an ECG machine that automatically calculates the heart rate and measures PR, QRS, QT, and QTc intervals. A 1-minute rhythm strip will also be obtained to screen out participants with arrhythmias at baseline. ECGs are required for screening only but may be repeated during the study if clinically indicated.

8.6.4.1 Additional Cardiac Screening

If the potential participant has cardiac risk factors (e.g., well-controlled hypertension, diabetes mellitus) and no other evidence of cardiovascular or cerebrovascular disease by history, physical exam or ECG, and if the investigator judges their overall health and other cardiovascular risk factors to be acceptable (family history, smoking, lipid levels, body weight, level of physical activity), they will be referred for stress test with either echocardiography or nuclear imaging, and for carotid ultrasound.

If these tests fail to reveal evidence of significant vascular disease or other cardiac disease, the person may be enrolled if there are no other contraindications. Additional cardiovascular testing to confirm eligibility may be performed in consultation with Medical Monitor. The investigators will record and review medications used to control hypertension prior to enrollment.

8.6.5 Clinical Laboratory Tests

Laboratory assessments, detailed in [Table 9: Protocol-required Screening Laboratory Tests](#), with the exception of urine pregnancy and drug tests, will be performed at a clinical laboratory near the study site. Clinical laboratories for each site will be specified in a separate document. Certificates and normal ranges will be stored in the site's Investigator Site File (ISF).

The site physician will confirm laboratory assessments gathered in screening for assessing eligibility. The site physician will use the list of normal ranges to conclude whether participants are eligible for the protocol and will indicate justification for admitting participants with abnormal values after consultation with the Medical Monitor.

The protocol does not prescribe any post-dosing clinical laboratory assessments. Additional clinical laboratory tests may be performed at any time during the study as determined necessary by the investigator or required by local regulations.

- If follow-up clinical labs are collected, record any clinically significant changes occurring during the study as an AE.
- All laboratory tests with values considered clinically significant during participation in the study should be repeated until the values are no longer considered clinically significant by the investigator or Medical Monitor.
 - If clinically significant values do not return to normal/baseline within a period of time judged reasonable by the investigator, the etiology should be identified, and the sponsor notified.
 - All protocol-required laboratory tests, as defined in [Table 9: Protocol-required Screening Laboratory Tests](#), must be conducted in accordance with the Laboratory Manual
 - If laboratory values from non-protocol-specified laboratory tests performed at the institution's local laboratory require a change in participant management or are considered clinically significant by the investigator (e.g., SAE or AE or dose modification), then the results must be recorded.

The maximum amount of blood collected from each participant over the duration of the study, including any extra assessments that may be required, should not exceed 20 mL.

Table 9: Protocol-required Screening Laboratory Tests

Laboratory Tests	Parameters
Hematology	
 • Hematocrit • Hemoglobin • Red Blood Cell (RBC) indices: 
 ○ RBC count ○ Percentage and absolute differential counts ○ Red cell distribution width (RDW) ○ Mean corpuscular volume (MCV) ○ Mean corpuscular hemoglobin (MCH) ○ Mean corpuscular hemoglobin concentration (MCHC) • White blood cell (WBC) indices: 
 ○ RBC count ○ Percentage and absolute differential counts ○ Neutrophils ○ Lymphocytes ○ Monocytes ○ Eosinophils ○ Basophils
Clinical chemistry	
 • Alanine aminotransferase (ALT)/serum glutamic-pyruvic transaminase (SGPT) • Albumin, serum • Albumin:Globulin (A:G) ratio • Alkaline phosphatase • Aspartate aminotransferase (AST)/serum glutamic-oxaloacetic transaminase (SGOT) • Bilirubin, total and direct • Blood urea nitrogen (BUN): creatinine ratio • Calcium, serum • Carbon dioxide • Chloride, serum • Globulin, total • Glucose, fasting • Potassium, serum • Protein, total, serum • Sodium, serum
Routine urinalysis	
 • Specific gravity, color, appearance • pH, glucose, protein, blood, ketones, bilirubin, urobilinogen, nitrite, leukocyte esterase by dipstick
Pregnancy testing	
 • Urine human chorionic gonadotropin (hCG) pregnancy test (for PABP only)¹
Other screening tests	
 • Thyroid Stimulating Hormone (TSH) with reflex free T3 and T4 • Urine drug screen (to include at minimum: amphetamines, barbiturates, cocaine, opiates, cannabinoids, and benzodiazepines)
¹ Local urine testing will be standard for the protocol unless serum testing is required by local regulation or IRB/IEC.	

Investigators must document their review of each screening laboratory report.

8.6.6 Pregnancy Testing

- Pregnancy testing is required for participants that are a person able to become pregnant (PABP) as defined in [Appendix 2: Contraceptive and Barrier Guidance](#).
- Pregnancy testing (urine or serum as required by local regulations) should be conducted at the time points as specified in the SoA.
- Pregnancy testing (urine or serum as required by local regulations) should be conducted at the end of relevant systemic exposure.
- Additional serum or urine pregnancy tests may be performed, as determined necessary by the investigator or required by local regulation, to establish the absence of pregnancy at any time during the participant's participation in the study.

8.6.7 Remote Visits

Some of the non-drug therapy sessions and online evaluations may be permitted remotely, via tele-assessment (online video meetings), rather than at the study site. Remote visits if deemed appropriate may be permitted based on prior experience or in the context of local regulation due to a pandemic. There may be benefits to remote visits, such as convenience and reduced risk of COVID-19 transmission. There may be risks, including potential breach of security and technological difficulties or interruptions.

8.7 Adverse Events, Serious Adverse Events, and Other Safety Reporting

The investigator and any qualified designees are responsible for detecting, documenting, and recording events that meet the definition of an Adverse Event (AE) or Serious Adverse Event (SAE) and remain responsible for following up on all AEs.

AEs will be reported by the participant (or, when appropriate, by a caregiver, surrogate, or the participant's legally authorized representative).

8.7.1 AE Definition

An AE is any untoward medical occurrence in a clinical study participant, temporally associated with the use of study intervention, whether or not considered related to the study intervention.

Note: An AE can therefore be any unfavorable and unintended sign (including an abnormal laboratory finding), symptom, or disease (new or exacerbated) temporally associated with the use of study intervention.

8.7.1.1 Events Meeting the AE Definition

- Any abnormal laboratory test results (hematology, clinical chemistry, or urinalysis) or other safety assessments (e.g., ECG, radiological scans, vital signs measurements), including those that worsen from baseline, considered clinically significant in the medical and scientific judgment of the investigator (i.e., not related to progression of any underlying disease).
- Exacerbation of a chronic or intermittent pre-existing condition including either an increase in frequency and/or intensity of the condition.
- New condition detected or diagnosed after study intervention administration even though it may have been present before the start of the study.

- Signs, symptoms, or the clinical sequelae of a suspected intervention-intervention interaction.
- Signs, symptoms, or the clinical sequelae of a suspected dosing error of either study intervention or a concomitant medication. A dosing error will not be reported as an AE/SAE unless it is an intentional overdose taken with possible suicidal/self-harming intent. Such overdoses should be reported regardless of sequelae.
- Lack of efficacy or failure of expected pharmacological action will not be reported as an AE or SAE. Such instances will be captured in the efficacy assessments. However, the signs, symptoms, and/or clinical sequelae resulting from lack of efficacy will be reported as AE or SAE if they fulfill the definition of an AE or SAE.

8.7.1.2 Events NOT Meeting the AE Definition

- Any clinically significant abnormal laboratory findings or other abnormal safety assessments that are associated with an underlying disease, unless judged by the investigator to be more severe than expected for the participant's condition or meet other prespecified reporting criteria.
- The disease/disorder being studied or expected progression, signs, or symptoms of the disease/disorder being studied, unless more severe than expected for the participant's condition.
- Medical or surgical procedure (e.g., endoscopy, appendectomy): the condition that leads to the procedure may fit the criteria for an AE.
- Situations in which an untoward medical occurrence did not occur (social and/or convenience admission to a hospital).
- Anticipated day-to-day fluctuations of pre-existing disease(s) or condition(s) present or detected at the start of the study that do not worsen.
- Expressions of emotion or other emotional descriptions which are consistent with what would be expected during a therapeutic interaction with a participant meeting the eligibility criteria related to PTSD, unless participant reports effects interfere with daily activities.
 - Limited examples of this include euphoria, positive mood, compassion for self, compassion for others, intellectual efficiency, calmness, talkative, open to new experiences, meaningful experience.

8.7.2 SAE Definition

An SAE is defined as any untoward medical occurrence that, at any dose, meets one or more of the criteria listed:

1. Results in death.
2. Is life threatening.
 - The term life threatening in the definition of SAE refers to an event in which the participant was at risk of death at the time of the event. It does not refer to an event, which hypothetically might have caused death, if it were more severe.
3. Requires inpatient hospitalization or prolongation of existing hospitalization.
 - In general, hospitalization signifies that the participant has been admitted (usually involving at least an overnight stay) at the hospital or emergency ward for observation and/or treatment that would not have been appropriate in the physician's office or outpatient setting. Complications that occur during hospitalization are AEs. If a complication prolongs hospitalization or fulfills any other serious criteria, the

- event is serious. When in doubt as to whether hospitalization occurred or was necessary, the AE should be considered serious.
- Hospitalization for elective treatment of a pre-existing condition that did not worsen from baseline is not considered an AE.
4. Results in persistent or significant disability/incapacity.
 - The term disability means a substantial disruption of a person's ability to conduct normal life functions.
 - This definition is not intended to include experiences of relatively minor medical significance such as uncomplicated headache, nausea, vomiting, diarrhea, influenza, and accidental trauma (e.g., sprained ankle) that may interfere with or prevent everyday life functions but do not constitute a substantial disruption.
 5. Is a congenital anomaly/birth defect.
 6. Other situations:
 - Medical or scientific judgment should be exercised by the investigator in deciding whether SAE reporting is appropriate in other situations such as significant medical events that may jeopardize the participant or may require medical or surgical intervention to prevent one of the other outcomes listed in the above definition. These events should usually be considered serious.

8.7.3 Adverse Events of Special Interest (AESI)

In accordance with the guidance Clinical Safety Data Management Definitions and Standards for Expedited Reporting ICH Topic E2A: Guidance for Industry or FDA Safety Reporting Requirements for INDs and BA/BE Studies, the sponsor will pay special attention to a subset of AEs. These AEs will be marked in the eCRF with the denotation "Adverse Event of Special Interest" (AESIs) whether serious or non-serious.

A subset of AEs will be collected in order to assess signals of cardiovascular risk for the IMP in the intended patient population that could be indicative of QT interval prolongation or cardiac arrhythmias, including Torsade de pointes, sudden death, ventricular extrasystoles, ventricular tachycardia, ventricular fibrillation and flutter, non-postural syncope, and seizures.

A subset of AEs involving suicide risk will be collected as AESIs whether serious or non-serious. These AESI terms include:

- Suicides
- Suicide attempts
- Self-injurious behavior associated with suicidal ideation
- Suicidal ideation judged to be serious or severe in the opinion of the investigator

In order to assess signals of abuse potential for the IMP in the intended patient population:

- AESIs involving the terms of Behavioral addiction, Drug abuser, Substance abuser, Dependence, Intentional product misuse, Overdose (accidental, intentional, or prescribed), or Drug diversion in cases that are related to MDMA or "Ecstasy" (unregulated material presented as MDMA) will be collected and coded as AESIs in the eCRF.
- Cases of noncompliance, protocol violations, participants lost to follow-up, and any other reasons why participants dropped out of the study will be assessed for presence of AESIs.
- Qualitative urine drug test data will be collected prior to each Experimental Session. Any positive findings that cannot be attributed to pre-approved concomitant medications or

diet will be reviewed by the Medical Monitor to assess compliance with ongoing eligibility criteria and for presence of AESIs.

If an AESI is a SAE or if it involves suicide risk, it should be reported within 24 hours of the site's awareness of the event.

8.7.4 Time Period and Frequency for Collecting AE and SAE Information

All SAEs will be collected from the signing of the ICF until the study termination visit at the timepoints.

All AEs will be collected from initial study enrollment (in participants who meet eligibility criteria following screening) until the study termination visit at the timepoints specified in SoA.

Medical occurrences that begin before the start of Visit 0 but after obtaining informed consent will be recorded as medical history/current medical conditions, not as AEs.

All SAEs will be recorded and reported to the sponsor or designee immediately and under no circumstance should this exceed 24 hours. The investigator will submit any updated SAE data to the sponsor within 24 hours of it being available.

Investigators are not obligated to actively seek information on AEs or SAEs after conclusion of the study participation. However, if the investigator learns of any SAE, including a death, at any time after a participant has been discharged from the study, and they consider the event to be reasonably related to the study intervention or study participation, the investigator must promptly notify the sponsor.

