7.2 Participant Discontinuation/Withdrawal from the Study

- A participant may withdraw from the study at any time at their own request or may be withdrawn at any time at the discretion of the investigator for safety, behavioral, or compliance reasons. This is expected to be uncommon.
- At the time of discontinuing from the study, if possible, an early discontinuation visit should be conducted..
- The participant will be permanently discontinued from the study intervention and the study at that time. The site team will provide the participant with a plan moving forward as described in [Section 8.4.4 Plan Moving Forward](#).
- If a participant develops any Exclusion Criteria that, in the opinion of the Medical Monitor or Site, affects the safety of the participant, the participant will discontinue treatment in Experimental Sessions but may remain in the study for any individual associated non-drug Therapy and Integrative Sessions.
- If a participant withdraws consent for disclosure of future information, the sponsor may retain and continue to use any data collected before such a withdrawal of consent.

- If a participant withdraws from the study, they may request destruction of any samples taken and not tested, and the investigator must document this in the site study records.
- If a participant withdraws, cohort will continue with reduced size.

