8.3.2 Telephone Contact After Experimental Sessions

A member of the therapy team will follow-up with the participant by telephone every other day for 14 days after each Experimental Session. Calls will not be made if there is an Integration Session scheduled the same day.

The goal of the telephone contact is to assess health changes, ensure participant safety, and offer support. Each call will last on average 5 to 15 minutes but could be longer to address participant concerns and to adequately assess wellbeing. Additional telephone contact can be initiated at the request of the therapy team or participant.

At each telephone contact, the therapy team will:

- Inquire about any possible changes in health, assess the participant's mental health and the status of any previously recorded AEs, and record AEs as described in [Section 8.7: Adverse Events, Serious Adverse Events, and Other Safety Reporting](#).
- Inquire about concomitant medication use and compliance.
- Offer support in accordance with the Treatment Manual.
- Administer the Since Last Visit C-SSRS.

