8.4.3 Study Termination

Study Termination will take place 1 week (0-9 days) after the final CAPS-5 assessment and can occur on the same day as Outcome visit. Participants who have withdrawn from treatment but have continued for follow-up will also complete this assessment immediately upon withdrawal.

After all Study Termination measures and assessments are completed, the participant is considered terminated from the study. The participant can resume normal everyday life. The study team will provide a plan moving forward, which may include a referral for additional medical or therapeutic care, as described in [Section 8.4.4 Plan Moving Forward](#). Eligible participants may be invited to participate in a future long-term follow-up (LTFU) extension study, which will be conducted under a separate protocol.

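### Active safety data collection has no minimum time after the last dose, and the protocol's sections disagree on whether it stops at once when a participant stops treatment

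*Protocol*

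**What the plan says.** **End of collection.** Section 8.7.4 states "All SAEs will be collected from the signing of the ICF until the study termination visit at the timepoints". AEs run from enrollment "until the study termination visit at the timepoints specified in SoA". No minimum time since the last dose is set. The section adds "Investigators are not obligated to actively seek information on AEs or SAEs after conclusion of the study participation", with one exception: the sponsor must be notified of a related event "if the investigator learns of any SAE, including a death, at any time after a participant has been discharged from the study".

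**Timing of the last visit.** For completers, "Study Termination will take place 1 week (0-9 days) after the final CAPS-5 assessment". For others, 8.4.3 states "Participants who have withdrawn from treatment but have continued for follow-up will also complete this assessment immediately upon withdrawal", and once that visit is done the participant is out of the study. Section 8.4.2 likewise has anyone withdrawn from treatment complete the final Outcome assessment as soon as they withdraw.

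**Status after stopping.** Section 7.1 lets a participant who stops study intervention stay in the study for the remaining individual sessions. Section 7.2 says much the same for someone who develops an exclusion criterion. For those leaving the study altogether, at their own request or by the investigator's decision, 7.2 states "The participant will be permanently discontinued from the study intervention and the study at that time".

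**Intended contact and data.** Section 8.3.2 states "A member of the therapy team will follow-up with the participant by telephone every other day for 14 days after each Experimental Session". Each call covers AEs and the C-SSRS. Section 6.3 aims for complete data, expressly including people who discontinue treatment.

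**Reporting.** Section 9.3.5 reports the number and percentage of participants with TEAEs. The safety set in 9.2 holds everyone exposed.

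**The concern.** The length of safety observation depends on when a visit takes place, and that visit moves with the decision to stop. A participant withdrawn from treatment the morning after an Experimental Session could complete Study Termination that day. The safety calls would then have no clear basis, although 8.3.2 plans them after every session and Table 1 lists phone contact in the following week as a mitigation for psychological distress, which it says may appear after the drug effect has gone.

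Safety is in the study title and there is no DMC. A crude percentage keeps an early leaver in the denominator whatever the length of observation, so new events after the cut-off can go unrecorded. The sections also disagree, so sites could handle the same situation differently.

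**Working it through.** **1. Planned collection for completers.** The protocol states no total, so there is no figure to reproduce. Inputs are the visit windows in days:

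| Interval | Source | Shortest | Nominal | Longest |
|---|---|---|---|---|
| Session 1 to Session 2 | 8.3.1, Table 6 | 21 | 28 | 35 |
| Session 2 to Integration 2.4 | 8.3.3, Table 7 | 17 | 21 | 28 |
| Integration 2.4 to Outcome | 8.4.1 | 14 | 28 | 42 |
| Outcome to Study Termination | 8.4.3 | 0 | 7 | 9 |

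- Last dose to Study Termination: 17 + 14 + 0 = 31; 21 + 28 + 7 = 56; 28 + 42 + 9 = 79 days.
- First dose to Study Termination: add 21, 28 and 35, giving 52, 84 and 114 days.
- Check against the 7 to 9 weeks in 8.3: Session 1 to Integration 2.4 is 28 + 21 = 49 days (7.0 weeks) nominal and 35 + 28 = 63 days (9.0 weeks) at most. The shortest windows give 38 days (5.4 weeks).

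**2. Collection after early withdrawal, read literally.** If the participant is withdrawn from treatment the morning after a session, 8.4.3 puts Study Termination on that day, about 1 day after dosing. About 7 calls (14 / 2) would be left undone, fewer where an Integration Session replaces a call.

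**3. A milder reading of 8.4.3.** Suppose withdrawal there means leaving follow-up. Section 8.4.2 carries no such qualifier, so the Outcome assessment is still immediate, and the ordinary 0 to 9 day window then puts Study Termination at day 1 + 9 = 10 at the latest. That is still short of 14.

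**4. Do other provisions look for new events?**
- 8.7.6.4 follows SAEs and AESIs already reported. It does not search for new ones.
- 8.7.3 reviews the reasons for dropping out for AESIs. It does not cover what happens later.
- 8.7.4 requires notice of related SAEs the investigator learns of. It does not cover non-serious events, or SAEs the site never hears about.

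**5. Effect on a reported percentage.** One participant of 18 is 100 / 18 = 5.6 points. With k participants cut off early, true incidence p over planned follow-up, and incidence q seen by the cut-off, the shift is [(18 − k)p + kq] / 18 − p = k(q − p) / 18. The protocol gives none of k, p or q, so these are assumptions:
- k = 1, p = 20%, 80% of events before the cut-off (q = 16%): 1 × (0.16 − 0.20) / 18 = −0.2 points.
- k = 3, p = 50%, constant hazard over 84 days, cut-off at day 1 (q = 1 − 0.5^(1/84) = 0.8%): 3 × (0.008 − 0.50) / 18 = −8.2 points.
- k = 0: no shift.

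**The case against.** Ending collection at the last visit is ordinary practice, and so is ending it when someone leaves the study. Sections 7.1, 7.2 and 6.3 point towards keeping people who only stop treatment under observation, so 8.4.3 may be no more than a drafting slip. Related SAEs learned of later must be notified, reported SAEs and AESIs are followed on, and dropouts are reviewed for AESIs. Section 7.2 expects withdrawal to be uncommon. The SoA, to which 8.7.4 refers, is not available here and may specify more.

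Much of this stands. Immediate termination is not the protocol's only rule, so the finding is a contradiction together with a missing floor. It does not stand as a full answer, because remaining in the study is only permitted, while 8.4.2 and 8.4.3 are worded as requirements and 8.4.3 names the very group that stayed. Leaving the study is also not the same as refusing contact: 7.2 allows the investigator to withdraw someone for safety, behavioral or compliance reasons and treats withdrawn consent for future information separately.

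A reader might infer that those most likely to have been harmed are watched least. The protocol does not support that: the listed reasons include the participant's own request, behavior and compliance, and no withdrawal rate is given. A reader might also infer that TEAE percentages will be biased low. The direction can only be downward, but an event that prompted withdrawal is already recorded, and that person already counts in the any-TEAE percentage. Only new terms or worsening severity can be lost. Someone who stops after Session 1 has also had only one exposure, so comparing their follow-up with 52 to 114 days overstates the gap.

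**Conclusion.** The point holds as an internal conflict with a practical consequence. Section 8.7.4 sets no minimum post-dose collection time, and 8.4.2 and 8.4.3 conflict with 7.1, 7.2, 6.3 and 8.3.2. On the literal text, active collection can stop about a day after dosing, against 31 to 79 days after the last dose for completers and the 14 days of calls. This applies to a dosed participant withdrawn from treatment, or withdrawn by the investigator without refusing contact.

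The percentages in 9.3.5 can then be too low, but the protocol does not allow the amount to be estimated. The −0.2 to −8.2 points above rest wholly on assumed inputs, and the effect is zero if nobody withdraws early or nothing new occurs afterwards. The conclusion assumes that the SoA does not already require later contact. It is worth correcting because the text as written gives a poorer safety record and the remedy is cheap.

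**What to change.** Reconcile 7.1, 7.2, 8.4.2, 8.4.3 and 8.7.4 so that, for anyone who has received IMP:

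- AE, SAE and C-SSRS data collection continues at least to the end of the 8.3.2 telephone schedule after their last dose.
- For those who stop treatment but remain in follow-up, collection continues to the scheduled Study Termination visit.
- Both apply unless the participant declines contact.

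This concerns data collection only and takes no position on when treatment should stop or who should be withdrawn.

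The cost is an amendment touching several sections and at most about 7 short calls, already planned, per early withdrawal. Some participants will decline them. For people who leave the study, a 14-day floor does not match the completers' 31 to 79 days. It secures the window the protocol already meant to observe, and the remaining difference in follow-up should be kept in mind when the percentages are read.
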